## 9.4 Stopping Rules

If the discontinuation rate due to toxicity is 20% or greater and the lower bound for the one-tailed 95% confidence interval is > 10%, this strategy would not be considered feasible. Six months after the 20th patient is enrolled and six months after the 40th patient is enrolled, we will assess the frequency of toxicity requiring permanent discontinuation of the drug. If there is a greater than 20% rate for discontinuation of drug due to toxicity during therapy at either time point, the study accrual will be suspended and we will assess the study design. Because the confidence interval may be calculated multiple times, the actual confidence level will be overstated. This increases the likelihood of rejecting the therapy due to toxicity. However, this is felt to be an acceptable risk in order to prevent continuation of a therapy that may have a toxicity rate that precludes its routine use.

If there is any treatment-related mortality event, the study accrual will be suspended until all data pertaining to the event is reviewed by the Study Chair and co-investigators.

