**Figure 2-1: Study Schema**

## 5 Population

The total number of patients enrolled in this study will be 105, with 35 patients in each of the three treatment arms.

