**Table 6-1b      Temozolomide dose levels**

Dose level	Dose and schedule
+1 (dose increased at cycle 2 at treating MD's discretion)	200 mg/m  /day for days 1-5 of each 28-day cycle
0 (starting dose)	150 mg/m  /day for days 1-5 of each 28-day cycle
-1	100 mg/m  /day for days 1-5 of each 28-day cycle
-2	75 mg/m  /day for days 1-5 of each 28-day cycle

If a patient has already decreased 2 dose levels of a specific drug, no further dose reduction is permitted. Patients who need an additional dose reduction will be required to discontinue the drug in question.

In the combination treatment arm, hematologic toxicity will initially be presumed due to temozolomide. Nausea, emesis and constipation during or within a few days after temozolomide dosing will be presumed due to temozolomide. Acneiform rash will be presumed due to everolimus; all other rash will initially be presumed due to temozolomide. Elevation of liver enzymes, hyperglycemia, hyperlipidemia, mucositis, diarrhea, and noninfectious pneumonitis will initially be presumed due to everolimus.

Treatment or visit delays for public holidays or weather conditions do not constitute a protocol violation.

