**Table 6-6 Management of non-infectious pneumonitis**

Worst grade pneumonitis	Suggested investigations	Management of pneumonitis	Everolimus dose adjustment
Grade 1	CT scans with lung windows.	No specific therapy is required	No dose adjustment required. Initiate appropriate monitoring.
Grade 2	CT scan with lung windows. Consider pulmonary function testing includes: spirometry, DLCO, and room air O 2 saturation at rest. Consider a bronchoscopy with biopsy and/or BAL. Monitoring at each visit until return to ≤ grade 1. Return to initial monitoring frequency if no recurrence.	Symptomatic only. Consider corticosteroids and/or other supportive therapy if symptoms are troublesome.	Rule out infection and consider interruption of everolimus until symptoms improve to Grade ≤ 1. Re-initiate everolimus at one dose level lower. Discontinue everolimus if failure to recover within ≤ 28 days.
Grade 3	CT scan with lung windows and pulmonary function testing includes: spirometry, DLCO, and room air O 2 saturation at rest. Monitoring at each visit until return to ≤ grade 1. Return to initial monitoring frequency if no recurrence. Bronchoscopy with biopsy and/or BAL is recommended.	Consider corticosteroids if infective origin is ruled out. Taper as medically indicated.	Rule out infection and interrupt everolimus until symptoms improve to Grade ≤ 1. Consider re-initiating everolimus at one dose level lower (approximately 50% lower than the dose previously administered depending on individual clinical circumstances) Discontinue everolimus if failure to recover within ≤ 28 days.
Grade 4	CT scan with lung windows and required pulmonary function testing, if possible, includes: spirometry, DLCO, and room air O 2 saturation at rest. Monitoring at each visit until return to ≤ grade 1. Return to initial monitoring frequency if no recurrence. Bronchoscopy with biopsy and/or BAL is recommended if possible.	Consider corticosteroids if infective origin is ruled out. Taper as medically indicated.	Rule out infection and discontinue everolimus.

For patients receiving both everolimus and temozolomide: if everolimus is stopped due to toxicity, patients may continue to be treated with temozolomide at the discretion of the treating investigator.

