### 9.5.1 Analysis Population

The study plan is to accrue 105 patients. It is anticipated that many low-grade glioma patients completing initial surgical resection will be eligible for enrollment and will choose to participate. Based on current patient volume in the UCSF neurologic-oncology clinic, it is expected that a minimum of 2 patients per month will be enrolled.

With enrollment of 2 patients per month, accrual can be completed in a 53 month period. With 38 months from the time of enrollment of the last accrued patient in order to assess PFS-38, the approximate duration of study is expected to be 91 months.

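### Section 9.4 applies one study-wide discontinuation rate, so excess toxicity in Arm 2, the only combination arm, is diluted by the two everolimus-alone arms

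*Combined protocol and SAP*

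**What the plan says.** Section 9.4 contains two criteria. The first defines feasibility: "If the discontinuation rate due to toxicity is 20% or greater and the lower bound for the one-tailed 95% confidence interval is > 10" percent, the strategy is judged not feasible. The second governs accrual, six months after the 20th and six months after the 40th patient is enrolled: "If there is a greater than 20% rate for discontinuation of drug due to toxicity during therapy at either time point", then "the study accrual will be suspended and we will assess the study design". The quantity reviewed is described only as follows: "we will assess the frequency of toxicity requiring permanent discontinuation of the drug". No arm, denominator or interval method is stated.

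Section 5 plans 105 patients, "with 35 patients in each of the three treatment arms". Under Section 4, Arms 1 and 3 receive everolimus alone and Arm 2 receives everolimus with temozolomide. Describing the safety of that combination is a secondary objective (Section 3).

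On what counts as stopping in Arm 2, Section 6.2.1 says: "In the combination treatment arm, hematologic toxicity will initially be presumed due to temozolomide". Section 6.2.2 adds that "if everolimus is stopped due to toxicity, patients may continue to be treated with temozolomide at the discretion of the treating investigator". Section 6.2.3 provides for the reverse case, in which temozolomide is stopped for toxicity and everolimus may go on.

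**The concern.** The study gives two regimens but monitors one rate. Section 9.4 says the rule is there to avoid continuing a therapy whose toxicity would rule out routine use. A single rate answers that question for a mixture that is two thirds everolimus alone. If the combination is the less tolerable regimen, its excess has to be large enough to carry the whole study over the boundary before accrual pauses. This is the only numeric toxicity boundary in the plan. What is at stake is whether the plan would prompt a review of the combination while patients are still being enrolled to it.

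**Working it through.** **Is the rule study-wide?** The text does not say so outright. However, the second look follows the 40th enrolled patient, no arm exceeds 35, and the action falls on accrual to the study. Only a study-wide rate fits both looks.

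**Counts needed.** Section 9.4 gives no operating characteristics to reproduce, so I start from its thresholds. The exact one-sided 95% lower limit for x events in n patients is the 5% quantile of a Beta(x, n − x + 1) distribution.

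- Suspension trigger (>20%): 5/20 and 9/40.
- Feasibility criterion (≥20% and exact limit >10%): 5/20 (limit 10.4%) and 8/40 (limit 10.4%).

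**Example at 40 patients, 13 of them in Arm 2.** Suppose 5/13 in Arm 2 and 2/27 elsewhere.

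- Pooled: (5 + 2)/40 = 17.5%. This is below 20%, so neither criterion is met whatever the interval method.
- Arm 2 alone: 5/13 = 38.5%. The exact limit is 16.6%. The Wald limit is 0.385 − 1.645 × √(0.385 × 0.615/13) = 16.3%. Either way Arm 2 meets the feasibility criterion.

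**Break-even.** With one third of patients in Arm 2, rate c on the combination and rate m on everolimus alone, the expected pooled rate is c/3 + 2m/3. Setting this to 20% gives c = 60% − 2m, that is 50%, 40% and 30% for m = 5%, 10% and 15%.

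**Chance of a pause at either look.** All rates are assumptions. Section 2.4 reports dose reductions (9 of 48), not discontinuations. Inputs: cumulative denominators of 20 and 40, each patient in Arm 2 with probability one third, binomial events. The Arm 2 check is the feasibility criterion with an exact limit. Results come from exact enumeration; a 400,000-trial simulation agreed within 0.2 points.

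| Everolimus alone / combination | Pooled >20% | Pooled feasibility | Pooled feasibility or Arm 2 check |
|---|---|---|---|
| 5% / 30% | 15% | 20% | 56% |
| 10% / 30% | 31% | 40% | 61% |
| 10% / 20% | 15% | 20% | 32% |
| 15% / 20% | 31% | 40% | 46% |
| 10% / 10% | 5.0% | 6.7% | 8.7% |
| 15% / 15% | 22% | 29% | 33% |
| 20% / 20% | 51% | 61% | 63% |

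The first step across each row comes from changing the criterion; only the second comes from the Arm 2 check.

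**Sensitivity to the Arm 2 share (5% / 30%).** The frequencies in Sections 2.3 and 7.3.2 imply a share of 0.70 × 0.50 = 35%. The 30% co-deletion figure is for all adult low-grade gliomas, while eligibility requires an IDH mutation, so the share is uncertain. At 25%, 35% and 40%, pooled feasibility gives 11%, 22% and 29%; with the Arm 2 check it gives 44%, 58% and 63%.

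**Sensitivity to the denominator.** Section 9.5.1 says "it is expected that a minimum of 2 patients per month will be enrolled". If everyone enrolled by the look date is counted, the denominators at that rate are 20 + 6 × 2 = 32 and 40 + 6 × 2 = 52. At 5% / 30% the result is 15% pooled (under both criteria) and 66% with the Arm 2 check.

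**Do the two criteria agree?** Not always. At 8/40 with an exact limit (10.4%), the feasibility criterion is met but the rate does not exceed 20%. At 5/20 with a Wald limit (9.1%), the rate exceeds 20% but the feasibility criterion is not met. Neither interval method removes the disagreement in general.

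**The case against.** **Existing oversight.** Treatment is open and each patient's arm is known. The Site Committee reviews toxicity with attribution (Section 8.4, Appendix 3), the DSMC meets every six weeks, any treatment-related death suspends accrual, and Section 9.6 tabulates discontinuations by arm. A reader might infer that the combination is unmonitored; the documents do not support that. What stands is narrower: none of these sets a discontinuation-rate boundary for the combination while accrual is open.

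**Which stops count.** Section 9.4 speaks of one drug, and everolimus is common to all arms. If only everolimus stops count, temozolomide stops in Arm 2 drop out and the Arm 2 excess may be small. This stands. The combination rates in the table then refer to everolimus stops only.

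**Assumed rates.** The 5% / 30% case favours the point. At 15% / 20%, 9 of the 15 points gained come from the change of criterion and only 6 from the Arm 2 check. Section 2.4 describes the combination as tolerable overall in its cited studies. Nothing in the documents shows that it will be stopped more often than everolimus alone, and this point does not claim so.

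**Extreme examples.** A reader might argue that even 8/13 in Arm 2 and none elsewhere escapes the rule, because 8/40 is exactly 20%. It escapes only the suspension trigger. With an exact limit, 8/40 meets the feasibility criterion.

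**Small numbers.** Arm 2 will have roughly 7 and 13 to 14 patients at the looks, and assignment by biomarker means this is not fixed. The Arm 2 check alone detects a true 20% in only about 24% of trials. That is a reason to add it to the pooled rule and not to substitute it.

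**Conclusion.** The point holds as a gap in design. Followed as written, Section 9.4 monitors a mixture of two regimens, and a combination-arm excess that would fail the protocol's own feasibility criterion can pass unnoticed by the rule. With looks at 20 and 40 and one third of patients in Arm 2, adding the check raises the chance of a pause from 20% to 56% at assumed rates of 5% / 30%, and from 40% to 61% at 10% / 30%. The gain falls to 6 points at 15% / 20% and 2 points at a uniform 20%. Its size therefore rests on rates the documents do not give, on the number in Arm 2 at each look, and on which drug's discontinuation is counted. The study-wide reading is an inference, but the 35-patient cap leaves no workable alternative. The mismatch between the two criteria and the unclear event definition are accompanying clarifications. This is an inexpensive improvement that should be made; it does not show that the study is unsafe.

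**What to change.** Keep the study-wide rule. At the same two looks, apply the feasibility criterion to Arm 2 alone (rate ≥20% and one-sided 95% lower limit >10%), name the exact limit, and read the required count from the actual Arm 2 number. For instance, 3/7, 4/13 or 4/14 would meet it; 2/7 or 3/14 would not.

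Clarify three things alongside:

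- use one criterion for both the feasibility statement and the suspension of accrual;
- state the denominator (the first 20 and 40 patients, or all enrolled by the look date);
- reconcile the singular drug in Section 9.4 with Sections 6.2.1, 6.2.2 and 6.2.3, so that it is clear which discontinuations count in Arm 2.

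The cost is protocol wording and one extra tabulation of data already collected, with no added looks. With a single feasibility criterion, false pauses rise from 6.7% to 8.7% when every arm is truly at 10% (5.0% under the present >20% trigger), and from 29% to 33% at 15% everywhere (22% under that trigger). A pause leads to review of the design, not termination, and Section 9.4 already accepts some added chance of rejecting the therapy for toxicity.

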## 9.5 Analysis Plans

For the first two arms, the primary endpoint will be 33-month progression-free survival (PFS-33) and for the third arm it will be 38-month PFS (PFS-38). Patients will be analyzed based on intention to treat. The primary analyses will be performed at the time the 33- (38-) month PFS is known for all patients.

### 9.5.1 Analysis Population

The study plan is to accrue 105 patients. It is anticipated that many low-grade glioma patients completing initial surgical resection will be eligible for enrollment and will choose to participate. Based on current patient volume in the UCSF neurologic-oncology clinic, it is expected that a minimum of 2 patients per month will be enrolled.

With enrollment of 2 patients per month, accrual can be completed in a 53 month period. With 38 months from the time of enrollment of the last accrued patient in order to assess PFS-38, the approximate duration of study is expected to be 91 months.

### 9.5.2 Analysis of Primary Endpoints

**33-(38-)month PFS:** Analyses will be performed after all enrolled patients have completed 33 (38) months on study, or whenever the progression status of all patients has been established, whichever comes first. The primary analysis will be based on Kaplan-Meier method. Kaplan-Meier estimates and the associated 95% CIs will be calculated for the 33-(38-)month PFS separately for the three arms. The Cox proportional hazards model will also be used to allow for adjustment of the prognostic factors including age, KPS, and extent of resection.

### 9.5.3 Analysis of Secondary Endpoints

Overall survival and objective response and seizure rate: The method described above for the analysis of PFS-33 and PFS-38 will be applied to the analysis of OS. Response is based on the best response, defined as the best objective status as assessed by the RANO criteria. The point estimate and the associated 2-sided 95% CI for both the response rate and the seizure rate will be calculated separately for the three arms. To assess the reduction in seizure rate we will compare the seizure rate on study to that experienced one month prior to enrolling in the study. We will follow the RANO LGG guideline (van den Bent, Wefel, et al 2011) which calls a 50% or more reduction number of monthly seizures an ‘improvement’; a 50% or more increase a ‘worsening’; and anything less than 50% in either direction a ‘stable seizure rate’.

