##### **Secondary objectives**

- 1) To assess overall and progression-free survival distributions (Arms 1, 2 & 3).
- 2) To assess the objective response rate to treatment (Arms 1, 2 & 3).
- 3) To further delineate the safety profile of the combination of everolimus and TMZ (Arm 2)
- 4) To assess whether treatment (Arms 1, 2 & 3) provides clinical benefit by reducing seizure frequency

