**Secondary Endpoints (for all arms):**

- 1) Median and distribution of overall survival (OS) and PFS
- 2) Objective Response Rate (ORR)
- 3) Number of adverse events related to combination treatment
- 4) Rate of Reduction in Seizures (as outlined in van den Bent, Wefel *et al.* 2011)

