### **6.3 Concomitant medications**

Patients must be instructed not to take any medications (over-the-counter or other products) during the protocol treatment period without prior consultation with the investigator. The investigator should instruct the patient to notify the study site about any new medications he/she takes after the start of study drug. All medications (other than study drug) and significant non-drug therapies (including physical therapy and blood transfusions) taken within 14 days of starting study treatment through the 30-day safety follow up visit should be reported on the CRF. In particular, corticosteroid dosing will be recorded as use of corticosteroids may affect the appearance of T2 changes on MRI imaging. In addition, the definition of response is based on corticosteroid use (see Section 7.2.3).

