**Cytochrome P450 and P-glycoprotein inhibitors/inducers/substrates**

Co-administration with strong inhibitors of CYP3A4 or PgP should be avoided; and may cause increased everolimus concentrations. For a current table of Substrates, Inhibitors and Inducers please access the following website:

<http://www.fda.gov/Drugs/DevelopmentApprovalProcess/DevelopmentResources/DrugInteractionsLabeling/ucm093664.htm>

Everolimus is metabolized by CYP3A4 in the liver and to some extent in the intestinal wall.

Therefore, the following are recommended:

- Co-administration with strong inhibitors of CYP3A4 (e.g., ketoconazole, itraconazole, ritonavir) or P-glycoprotein (PgP) inhibitor should be avoided.
- Co-administration with moderate CYP3A4 inhibitors (e.g., erythromycin, fluconazole) or PgP inhibitors should be used with caution. If a patient requires co-administration of moderate CYP3A4 inhibitors or PgP inhibitors, reduce the dose of everolimus. Additional dose reductions may be required to manage toxicities. If the inhibitor is discontinued, the everolimus dose should be returned to the dose used prior to initiation of the moderate CYP3A4/PgP inhibitor after a washout period of 2 to 3 days.
- Grapefruit or citrus juices affect P450 and PgP activity. Concomitant use should be avoided.
- Co-administration with strong inducers of CYP3A4 should be avoided. If a patient requires co-administration of strong CYP3A4 inducers (i.e., phenytoin, carbamazepine, rifampin, rifabutin, phenobarbital, St. John's wort), an increase in the dose of everolimus up to twice the currently used daily dose should be considered, 5 mg increments. Enzyme induction usually occurs within 7-10 days; therefore everolimus dose should be increased by one increment 7 days after the start of the inducer therapy. If no safety concerns are seen within the next 7 days, the dose can be increased again one additional increment up to a maximum of twice the daily dose used prior to initiation of the strong CYP3A4 inducer.
- This dose adjustment of everolimus is intended to achieve similar AUC to the range observed without inducers. However, there are no clinical data with this dose adjustment in patients receiving strong CYP3A4 inducers. If the strong inducer is discontinued the everolimus dose should be returned to the dose used prior to initiation of the strong CYP3A4/PgP inducer.

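### The seizure endpoint (Section 9.5.3) takes no account of changes in anti-seizure drugs, so these can be counted as benefit or harm of study treatment

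*Combined protocol and SAP*

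**What the plan says.** - **Objective and endpoint (Section 3).** The fourth secondary objective is "To assess whether treatment (Arms 1, 2 & 3) provides clinical benefit by reducing seizure frequency". The matching endpoint is "Rate of Reduction in Seizures", defined by reference to a published response guideline for low-grade glioma.
- **Analysis (Section 9.5.3).** For each patient, "we will compare the seizure rate on study to that experienced one month prior to enrolling in the study". The plan says it follows the guideline, "which calls a 50% or more reduction number of monthly seizures an" improvement; a rise of the same size is a worsening, and anything between is stable. A point estimate and two-sided 95% CI "for both the response rate and the seizure rate will be calculated separately for the three arms". There is no test and no adjustment.
- **Inducers (Section 6.3.1).** "Co-administration with strong inducers of CYP3A4 should be avoided". The same bullet then provides for use: "If a patient requires co-administration of strong CYP3A4 inducers (i.e., phenytoin, carbamazepine, rifampin, rifabutin, phenobarbital, St. John's wort"), followed by an everolimus dose adjustment. Section 6.3.2 prohibits nothing.
- **Recording (Section 6.3).** Medications "taken within 14 days of starting study treatment through the 30-day safety follow up visit should be reported on the CRF".

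**The concern.** This is the only secondary objective worded as clinical benefit, and it is assessed by a before/after comparison within each patient, with no control group. Anti-seizure drugs act directly on the outcome. The rule looks at counts alone, so two patients with the same fall in seizures are classed alike even if one of them had an anti-seizure drug added in between. The reverse holds for a patient whose drug was reduced or stopped and who then had more seizures.

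Such changes are to be expected. Everolimus is given in all three arms, so the advice on strong inducers reaches every patient who takes phenytoin, carbamazepine or phenobarbital. It takes effect around the start of everolimus, close to the boundary between the two periods being compared. Apart from that advice, treatment lasts up to 24 cycles of 28 days (24 × 28 = 672 days), which leaves ample time for ordinary changes in anti-seizure treatment. At stake is whether the reported improvement rate can be read as evidence on this objective.

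**Working it through.** The documents give no expected rate, sample size or power for the seizure endpoint, so there is no planned figure to reproduce. The check rests mainly on the text.

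**1. Does any other section supply the missing condition?** The plan handles the same problem differently for imaging response.

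| | Imaging response | Seizure response |
|---|---|---|
| Drug that can alter the measure | Corticosteroids | Anti-seizure drugs |
| Recorded on the CRF | Yes, singled out in 6.3 | Yes, as a general concomitant drug |
| Condition in the definition | Yes: 7.2.3 requires a dose no higher than at baseline for partial and minor response, and none or physiological replacement only for complete response | None in 9.5.3 |
| Separate category or sensitivity analysis | Not needed, as the condition is built in | None |

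Section 9.5.4 adjusts the exploratory imaging models for confounders, but nothing comparable is planned for seizures.

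**2. Does the CRF window cover the baseline month?** Take a month as 30 days, and let d be the number of days from enrolment to first dose. The window opens 14 days before first dose, so it covers max(0, 14 − d) days of the baseline month.
- d = 0: 14 days covered, 30 − 14 = 16 not covered.
- d = 14 or more: no day covered.

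The Glossary ties enrolment to informed consent, and screening follows consent, so d will usually exceed 0. A drug started earlier and still taken inside the window is recorded. What can be missed is a drug stopped, or a dose changed, during the baseline month but before the window opens.

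**3. How large could the effect be?** All inputs here are assumptions. Let q be the share of patients with a change in anti-seizure drugs, a the improvement rate among them, and b the rate among the others. With no effect of study treatment, the observed rate is q·a + (1 − q)·b, and the part due to drug changes is q·(a − b). Take b = 10%.
- q = 10%, a = 30%: 0.10 × 0.20 = 2 points (observed rate 12%).
- q = 50%, a = 50%: 0.50 × 0.40 = 20 points (observed rate 30%).
- If changes make improvement less likely, the limit is a = 0, giving −q·b: −1 point at q = 10% and −5 points at q = 50%.

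The confidence interval does not reveal this. With 7 of 35 improved, the exact 95% CI is 8% to 37%, which reflects sampling error only. Thirty-five is the whole arm; patients without baseline seizures cannot show a 50% fall, so the usable number is smaller and the interval wider.

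**4. What would a condition on drugs leave unsolved?** Suppose seizures follow a Poisson distribution with a constant mean of λ per month, the baseline month has at least one, and the on-study average equals λ. The chance of being classed as improved with no change of any kind is P(K ≥ 2λ) / P(K ≥ 1): 42% at λ = 1, 17% at λ = 2, 5% at λ = 4 and 1% at λ = 8. A one-month baseline therefore produces false improvements in patients with few seizures, even on stable drugs.

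**The case against.** The other side has several sound points.

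- **No forced switch.** A reader might infer that the protocol moves patients off their anti-seizure drugs at study entry. It does not. The inducer text is advice, the same bullet provides for use if required, no eligibility criterion or washout concerns these drugs, and the prohibited list is empty. A switch completed before the baseline month would not confound the comparison. The documents do not say how many patients take these drugs.
- **The data are mostly there.** A reader might also infer that these drugs go unrecorded or can be changed without oversight. Sections 6.3 and 6.3.1 require patients to consult the investigator before taking any medication and the team to ask about new ones at each visit. Section 7.1.2 requires concomitant drugs and doses to be documented. The gap is in the analysis, plus a limited part of the baseline month.
- **The guideline may deal with it.** The endpoint is defined by reference to a publication that cannot be examined here. It may address anti-seizure drugs. That would not settle the matter, because the rule restated in 9.5.3 uses counts only, and an analyst following that text would apply no such condition.
- **Attribution is weak in any case.** There is no control arm, treatment begins within 120 days of surgery, and the baseline is one month. Holding anti-seizure drugs stable removes none of this. A drug change is also a post-baseline event, so conditioning on it does not yield a causal estimate.

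The last point limits what the fix may claim, but does not make the planned rate easier to interpret.

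**Conclusion.** The point holds as a gap in the analysis rule. As restated in 9.5.3, the seizure classification can count the result of an anti-seizure drug change as benefit or harm of study treatment. The protocol makes such changes foreseeable, and nothing planned would separate them out.

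The size and direction of the bias are unknown. The range of −5 to +20 points rests entirely on assumed values of q, a and b and shows only that the bias could matter beside an interval of 8% to 37%. A reader might go further and infer that the improvement rate is inflated, or that fixing this would make it attributable to everolimus. The documents support neither: a change can push the rate either way, and the other limits on attribution remain.

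The matter is worth correcting but not critical. The endpoint is secondary and descriptive, with no test or decision attached, and PFS-33 and PFS-38 are unaffected.

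**What to change.** **Section 9.5.3.** Keep the planned rate and add, for example:

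> Among patients with at least one seizure in the baseline month, the following will also be reported by arm: (a) improvement without any anti-seizure drug having been added, switched or raised since the start of the baseline month; (b) worsening without any anti-seizure drug having been reduced, stopped or switched since then; and (c) patients with any change in anti-seizure drugs, shown separately by direction of change and seizure category.

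Use all patients in the arm with baseline seizures as the denominator for (a) and (b), so that nobody is dropped because of a later event. A patient who improved while a drug was reduced counts in (a) and also appears in (c), so the lines are not to be added up. On this denominator, the planned rate minus (a) shows how many improvements came with escalation, which replaces the assumed figures above with observed ones. Describe (a) as improvement without anti-seizure drug escalation, not as improvement due to study treatment. If the cited guideline already has a rule on these drugs, state it in the text.

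**Section 6.3.** For anti-seizure drugs and their doses, extend the CRF look-back to the full month before enrolment.

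**Cost.** A short addition to the analysis text and a longer look-back for one drug class on an existing form. The headline improvement rate may be lower and the subgroups will be small. Patient care does not change.
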